#### 7.1.4. Interim Analysis

##### 7.1.4.1. Overview of Planned Analyses

No interim analysis is planned for this study.

## 8. SECONDARY STATISTICAL ANALYSES

### 8.1. Safety Analyses

The safety analyses will be based on the “All Subjects” population, unless otherwise specified.

Table 5 provides an overview of the planned analyses, with further details of data displays being presented in Appendix 10: List of Data Displays.

**Table 5 Overview of Planned Safety Analyses**

| Display Type                     | Absolute |   |            |   | Change from Baseline |   |            |       |
|----------------------------------|----------|---|------------|---|----------------------|---|------------|-------|
|                                  | Summary  |   | Individual |   | Summary              |   | Individual |       |
|                                  | T        | F | F          | L | T                    | F | F          | L     |
| Exposure                  |          |   |            |   |                      |   |            |       |
| Exposure Data                    |          |   |            |   | Y                    |   |            |       |
| AEs                       |          |   |            |   |                      |   |            |       |
| All AEs                          | Y        |   |            |   | Y                    |   |            |       |
| All Drug-Related AEs             | Y        |   |            |   | Y                    |   |            |       |
| Common Non-serious AEs           | Y        |   |            |   |                      |   |            |       |
| Serious AEs                      | Y        |   |            |   | Y                    |   |            |       |
| Withdrawal AEs                   |          |   |            |   | Y                    |   |            |       |
| Laboratory Values         |          |   |            |   |                      |   |            |       |
| Clinical Chemistry               |          |   |            |   | Y [2]                | Y |            |       |
| Hematology                       |          |   |            |   | Y [2]                | Y |            |       |
| Urinalysis (Dipstick)            | Y        |   |            |   | Y [2]                |   |            |       |
| Electrocardiograms (ECGs) |          |   |            |   |                      |   |            |       |
| ECG Findings                     | Y        |   |            |   | Y [3]                |   |            |       |
| ECG Values                       |          |   |            |   | Y [4]                |   |            |       |
| Vital Signs               |          |   |            |   |                      |   |            |       |
| Vital Signs                      |          |   |            |   | Y [4]                | Y |            | Y [4] |
| Liver                     |          |   |            |   |                      |   |            |       |
| Liver Events [1]                 |          |   |            |   | Y                    |   |            |       |

**NOTES :**

1. Conditional display, it will only be produced when an event has occurred.
2. Displays contain only subjects with DAIDS toxicities for HIV-infected patients of Grade 2 or higher
3. Displays contain only subjects with abnormal findings
4. Displays contain only subjects with values of potential clinical importance
  - T = Table, F = Figure, L = Listing, Y = Yes display generated.
  - Summary = Represents TFL related to any summaries (i.e. descriptive statistics) of the observed raw data.
  - Individual = Represents TFL related to any displays of individual subject observed raw data.

### 8.2. Exploratory Analyses

The exploratory analyses will be based on the “All Subjects” population, unless otherwise specified.

Table 6 provides an overview of the planned analyses, with further details of data displays being presented in Appendix 10: List of Data Displays.

**Table 6      Overview of Planned Exploratory Analyses**

| Display Type                       | Absolute |   |            |   |
|------------------------------------|----------|---|------------|---|
|                                    | Summary  |   | Individual |   |
|                                    | T        | F | F          | L |
| Palatability                |          |   |            |   |
| Palatability Questionnaire Results | Y        |   |            | Y |

**NOTES :**

- T = Table, F = Figure, L = Listing, Y = Yes display generated.
- Stats Analysis = Represents TFL related to any formal statistical analyses (i.e. modelling) conducted.
- Summary = Represents TFL related to any summaries (i.e. descriptive statistics) of the observed raw data.
- Individual = Represents FL related to any displays of individual subject observed raw data.

## 10. APPENDICES

| Section                                                                                         | Appendix                                                                                                                                                                                                                                                     |
|-------------------------------------------------------------------------------------------------|--------------------------------------------------------------------------------------------------------------------------------------------------------------------------------------------------------------------------------------------------------------|
| RAP Section 5 : General Considerations for Data Analyses & Data Handling Conventions |                                                                                                                                                                                                                                                              |
| Section 10.1                                                                                    | Appendix 1: Time and Events                                                                                                                                                                                                                                  |
| Section 10.2                                                                                    | Appendix 2: Treatment States & Phases                                                                                                                                                                                                                        |
| Section 10.3                                                                                    | Appendix 3: Data Display Standards & Handling Conventions 

• Study Treatment & Sub-group Display Descriptors

• Baseline Definitions & Derivations

• Reporting Process & Standards

 |
| Section 10.4                                                                                    | Appendix 4: Derived and Transformed Data 

• General, Study Population & Safety

• Pharmacokinetic

• Exploratory

                                                                            |
| Section 10.5                                                                                    | Appendix 5: Premature Withdrawals & Handling of Missing Data 

• Premature Withdrawals

• Handling of Missing Data

                                                                                      |
| Section 10.6                                                                                    | Appendix 6: Values of Potential Clinical Importance                                                                                                                                                                                                          |
| Section 10.7                                                                                    | Appendix 7: Multiple Comparisons and Multiplicity                                                                                                                                                                                                            |
| Section 10.8                                                                                    | Appendix 8: Model Checking and Diagnostics for Statistical Analyses                                                                                                                                                                                          |
| Other RAP Appendices                                                                     |                                                                                                                                                                                                                                                              |
| Section 10.9                                                                                    | Appendix 9: Abbreviations & Trade Marks                                                                                                                                                                                                                      |
| Section 10.10                                                                                   | Appendix 10: List of Data Displays                                                                                                                                                                                                                           |

## 10.1. Appendix 1: Time & Events

### 10.1.1. Protocol Defined Time & Events

| Assessments                  | All Study Periods (Parts 1 and 2) |                                                       |      |                                                                                      |       |       | Follow-up | Notes                                                                     |
|------------------------------|-----------------------------------|-------------------------------------------------------|------|--------------------------------------------------------------------------------------|-------|-------|-----------|----------------------------------------------------------------------------------|
|                              | Day -1                            | Day 1                                                 |      | Day 2                                                                                | Day 3 | Day 4 |           |                                                                                  |
|                              |                                   | Pre-dose                                              | 0 hr | Post Dose                                                                            | 24 hr | 48 hr |           |                                                                                  |
| Admission to Unit            | X                                 |                                                       |      |                                                                                      |       |       |           |                                                                                  |
| Discharge                    |                                   |                                                       |      |                                                                                      |       | X     |           |                                                                                  |
| Outpatient Visit             |                                   |                                                       |      |                                                                                      |       |       | X         | Follow-up visit will occur 7 to 10 days post last dose.                          |
| 12-lead ECG (single)         | X                                 |                                                       |      |                                                                                      |       |       |           |                                                                                  |
| Vital signs                  | X                                 | X                                                     |      | X                                                                                    |       | X     | X         | Single vital sign measurements performed at all time points.                     |
| Brief Physical Exam          | X                                 |                                                       |      |                                                                                      |       |       |           |                                                                                  |
| Urine Drug/Alcohol/Cotinine  | X                                 |                                                       |      |                                                                                      |       |       |           |                                                                                  |
| Pregnancy test (urine; WCBP) | X                                 |                                                       |      |                                                                                      |       |       | X         |                                                                                  |
| Clinical laboratory tests    | X                                 |                                                       |      | X                                                                                    |       |       | X*        |                                                                                  |
| Dosing                       |                                   |                                                       | X    |                                                                                      |       |       |           | See Protocol Section 7.1                                                         |
| Palatability Assessment      |                                   |                                                       |      | Start w/in 10 min post-dose                                                          |       |       |           | Complete for each dispersion treatment C (see Protocol Section 12.8, Appendix 8) |
| PK Sampling                  |                                   | X                                                     |      | Collect at: 0.5, 1, 1.5, 2, 2.5, 3, 4, 5, 6, 8, 12, 16, 24, 48 and 72 hrs post-dose. |       |       |           | Pre-dose (within 15 minutes prior to dosing), Protocol Section 9.4               |
| Meals                        |                                   | Fasted from 10 hrs prior to dosing to 4 hrs post-dose |      | Standard for the study center                                                        |       |       |           | See also Protocol Section 6.3.2 and Section 6.3.3                                |
| Adverse Events / SAE         | X                                 | <=====X=====<                                         |      |                                                                                      |       | X     |           |                                                                                  |
| Concomitant medications      | X                                 | <=====X=====<                                         |      |                                                                                      |       | X     |           |                                                                                  |

## 10.2. Appendix 2: Treatment States and Phases

### 10.2.1. Treatment States

Assessments and events will be classified according to time of occurrence relative to the start and/or stop date of the study treatment.

#### 10.2.1.1. Treatment States for Safety Data

| Treatment State | Definition                                                                                   |
|-----------------|----------------------------------------------------------------------------------------------|
| Pre-Treatment   | Date/Time $\leq$ Study Treatment Start Date/Time                                             |
| On-Treatment    | Study Treatment Start Date/Time $<$ Date/Time $\leq$ Study Treatment Stop Date/Time + 6 days |
| Post-Treatment  | Date/Time $>$ Study Treatment Stop Date/Time + 6 days                                        |

**NOTES:**

- If the study treatment stop date is missing then the assessment will be considered to be On-Treatment

#### 10.2.1.2. Treatment States for AE Data

| Treatment State                              | Definition                                                                                                                                                                                                 |
|----------------------------------------------|------------------------------------------------------------------------------------------------------------------------------------------------------------------------------------------------------------|
| Pre-Treatment                                | AE Start Date $<$ Study Treatment Start Date                                                                                                                                                               |
| On-Treatment                                 | If AE onset date is on or after treatment start date & on or before treatment stop date with 7 days lag time.
Study Treatment Start Date $\leq$ AE Start Date $\leq$ Study Treatment Stop Date + 6 days |
| Post-Treatment                               | If AE onset date is after the treatment stop date with 6 days lag time.
AE Start Date $>$ Study Treatment Stop Date + 6 days                                                                            |
| Onset Time Since 1 st Dose (Days) | If Treatment Start Date $>$ AE Onset Date = AE Onset Date – Treatment Start Date
If Treatment Start Date $\leq$ AE Onset Date = AE Onset Date – Treatment Start Date + 1
Missing otherwise.          |
| Duration (Days)                              | AE Resolution Date – AE Onset Date + 1                                                                                                                                                                     |
| Drug-related                                 | If relationship is marked 'YES' on eCRF OR value is missing.                                                                                                                                               |

**NOTES:**

- If the study treatment stop date is missing then the AE will be considered to be On-Treatment.

### 10.3. Appendix 3: Data Display Standards & Handling Conventions

#### 10.3.1. Study Treatment & Sub-group Display Descriptors

| Treatment Group Descriptions |                 |                                                                                                      |                             |                      |
|------------------------------|-----------------|------------------------------------------------------------------------------------------------------|-----------------------------|----------------------|
| Study Part                   | Treatment Group |                                                                                                      | Data Displays for Reporting |                      |
|                              | Code            | Description                                                                                          | Description   | Order  |
| 1                            | A               | DTG conventional 10 mg tablets (5 tablets) administered direct to mouth (test)                       | Treatment A                 | 1                    |
| 1                            | B               | DTG conventional 50 mg tablet administered direct to mouth (reference)                               | Treatment B                 | 2                    |
| 2                            | C               | DTG dispersible 5-mg tablets (5 tablets) administered as a dispersion and immediately taken (test 1) | Treatment C                 | 3                    |
| 2                            | D               | DTG dispersible 5-mg tablets (5 tablets) administered direct to mouth (test 2)                       | Treatment D                 | 4                    |
| 2                            | E               | DTG conventional 25 mg tablet administered direct to mouth (reference)                               | Treatment E                 | 5                    |

**NOTES:**

1. The word "Treatment" may be omitted from displays in order to limit wrapping
2. Order represents treatments being presented in TFL, as appropriate.

#### 10.3.2. Baseline Definition & Derivations

##### 10.3.2.1. Baseline Definitions

For all endpoints (except as noted in baseline definitions) the baseline value will be the latest pre-dose assessment. Baseline definitions are applicable to each period.

| Parameter          | Study Assessments Considered As Baseline |        |                  | Baseline Used in Data Display |
|--------------------|------------------------------------------|--------|------------------|-------------------------------|
|                    | Screening                                | Day -1 | Day 1 (Pre-Dose) |                               |
| Safety      |                                          |        |                  |                               |
| Hematology         | X                                        | X      |                  | Day -1                        |
| Clinical Chemistry | X                                        | X      |                  | Day -1                        |
| 12-Lead ECG        | X                                        | X      |                  | Day -1                        |
| Vital Signs        | X                                        | X      | X                | Day 1 (Pre-Dose)              |

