2.2. Time and Events Table

Table 2 Treatment Period Time and Events

Assessments	All Study Periods (Parts 1 and 2)						Follow-up	Notes			
	Day -1	Day 1		Day 2	Day 3	Day 4					
		Pre-dose	0 hr	Post Dose	24 hr	48 hr					
Admission to Unit	X										
Discharge						X					
Outpatient Visit							X	Follow-up visit will occur 7 to 10 days post last dose.			
12-lead ECG (single)	X										
Vital signs	X	X		X		X	X	Single vital sign measurements performed at all time points.			
Brief Physical Exam	X										
Urine Drug/Alcohol/Cotinine	X										
Pregnancy test (urine; WCBP)	X						X				
Clinical laboratory tests	X			X			X*	*Clinical laboratory tests at follow-up are only necessary if subject had a previous abnormal lab value			
Dosing		X						See Section 7.1			
Palatability Assessment				Start within 10 min after dose				Complete for each dispersion treatment C (see Section 12.8, Appendix 8)			
PK Sampling		X		Collect at: 0.5, 1, 1.5, 2, 2.5, 3, 4, 5, 6, 8, 12, 16, 24, 48 and 72 hrs post-dose.				Pre-dose (within 15 minutes prior to dosing), Section 9.4			
Meals	Fasted from 10 hrs prior to dosing to 4 hrs post-dose		Standard for the study center					See also Section 6.3.2 and Section 6.3.3			
Adverse Events / SAE	X	←=====X=====→				X					
Concomitant medications	X	←=====X=====→				X					

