5.2. Treatment Groups and Duration

The study treatments to be administered in Part 1 of the study are:

- Treatment A: Conventional 10-mg DTG tablet (5 tablets, test) administered direct to mouth.
- Treatment B: Conventional 50-mg DTG tablet (reference) administered direct to mouth.

Table 3 Part 1 – Two-Period Crossover

Sequence (Total N=14)	Period 1	Period 2
1 (n=7)	A	B
2 (n=7)	B	A

The study treatments to be administered in Part 2 of the study are:

- Treatment C: 5-mg dispersible DTG tablet (5 tablets) administered as a dispersion and immediately taken (test 1).
- Treatment D: 5-mg dispersible DTG tablet (5 tablets) administered as *direct to mouth* (test 2).
- Treatment E: Conventional 25-mg DTG tablet administered as direct to mouth (reference).

Table 4 Part 2 – Three-Period Crossover

Sequence (Total N=24)	Period 1	Period 2	Period 3
1 (n=4)	C	D	E
2 (n=4)	D	E	C
3 (n=4)	E	C	D
4 (n=4)	C	E	D
5 (n=4)	D	C	E
6 (n=4)	E	D	C

The total duration of participation for a subject participating in Part 1 of the study will be approximately 7 to 8 weeks, and for a subject participating in Part 2 of the study, the total duration will be 8 to 9 weeks.

Each participant will have a screening visit within 30 days prior to the first dose of study drug, two treatment periods each for a subject participating in Part 1 of the study and three treatment periods each for a subject participating in Part 2 of the study, with a single dose of study drug per treatment period and a follow-up visit within 7-10 days after the last dose of study drug. At Follow-up, male subjects with no ongoing adverse events (AEs) or Vital Sign/Laboratory measures of clinical concern may be followed virtually by the site via telephone contact.

To ensure adequate washout, there will be at least 7 days between dosing periods, with an allowance window of 4 hrs (i.e., 7 days minus 4 hrs) to allow for flexibility in scheduling subjects to dose at the clinic.

PK samples will be collected for 72 hrs after each dose of study drug.

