6.3.2. Fasting Conditions

During the overnight period from Day -1 to Day 1 of each dosing period:

- An evening meal and/or snack will be provided by the unit (e.g. on Day -1).
- Subjects must then fast from all food and drink (except water) for 10 hrs pre-dose and prior to any clinical laboratory evaluations (except repeat evaluations).
- Water is permitted with dosing (200-250 mL) for all Treatments except Treatment C and at all times except 1 hour (hr) pre-dose through 2-hrs post-dose.
- No food is allowed for at least 4 hrs post-dose.

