10.3. Key Elements of Analysis Plan

Final analyses will be performed after the completion of the study and final database authorization.

Data will be listed and summarized according to GlaxoSmithKline reporting standards where applicable. Listings will be sorted by subject, period, day, and time, noting treatment. Summaries will be presented by treatment, day and time.

Unless stated otherwise, descriptive summaries for continuous variables will include n, mean, standard deviation (SD), median, minimum, maximum; whereas, n and percent will be used as summary statistics for categorical variable. Geometric mean with associated 95% CI, and the between-subject coefficient of variance (CV) (%CVb) for the geometric mean will be included for PK variables, where applicable.

Baseline or pre-dose assessment is the last available assessment prior to time of the first dose unless it is specified otherwise. If there are multiple assessments collected on the same scheduled time, the average of these assessments will be used. For tabulated safety summaries, only the scheduled assessments will be included in the summary tables.

Version 9.4 or higher of the Statistical Analysis Software (SAS) system will be used to analyze data as well as to generate tables, listings, and figures.

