## 2. SUMMARY OF KEY PROTOCOL INFORMATION

### 2.1. Changes to the Protocol Defined Statistical Analysis Plan

The parameter “t” in the list of secondary endpoints in the protocol has been excluded as this does not represent an actual PK parameter and may be a typographical error in the protocol text. There were no other changes to or deviations from the originally planned statistical analysis specified in the protocol (Dated: 23/FEB/2017).

Listings of clinical laboratory data above a certain DAIDs toxicity grading are included in the outputs. Section 3.3.1 of the protocol indicated that these listings contain toxicities of grade 3 or higher; however, the listings will instead contain toxicities of grade 2 or higher.

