### 10.3.2.2. Derivations and Handling of Missing Baseline Data

| Definition           | Reporting Details                  |
|----------------------|------------------------------------|
| Change from Baseline | = Post-Dose Visit Value – Baseline |

NOTES :

- Unless otherwise specified, the baseline definitions specified in Section 10.3.2.1 Baseline Definitions will be used for derivations for endpoints / parameters and indicated on summaries and listings.
- Unless otherwise stated, if baseline data is missing no derivation will be performed and will be set to missing.
- The baseline definition will be footnoted on all change from baseline displays.

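### Tables 2.5 and 2.6 use the next period's Day -1 laboratory value, the only scheduled late sample after a non-final dose, solely as the next treatment's baseline, so a delayed rise enters no treatment's summarised change

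*SAP*

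**What the plan says.** The Time and Events table (Protocol 2.2) applies to all periods of both parts. It schedules clinical laboratory tests on Day -1 and at one early point after dosing. A further test at the follow-up visit after the last dose is conditional: "Clinical laboratory tests at follow-up are only necessary if subject had a previous abnormal lab value". That each period has its own Day -1 is confirmed by the fasting rules (Protocol 6.3.2), which apply "During the overnight period from Day -1 to Day 1 of each dosing period". On spacing, Protocol 5.2 says "there will be at least 7 days between dosing periods, with an allowance window of 4 hrs".

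SAP 10.3.2.1 states that "the baseline value will be the latest pre-dose assessment. Baseline definitions are applicable to each period"; its table gives Day -1 as the displayed baseline for haematology and clinical chemistry. SAP 10.3.2.2 defines change as "Post-Dose Visit Value – Baseline". Tables 2.5 (chemistry) and 2.6 (haematology) summarise that change, with no programming notes.

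SAP 10.2.1.1 ends the on-treatment state for safety data at "Study Treatment Stop Date/Time + 6 days". It does not say whether start and stop are taken per period, and no laboratory display is said to use this window.

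**The concern.** Each period gives one early post-dose laboratory value, and change is computed from that value alone. The next Day -1 sample then does two jobs: it is a baseline for the coming treatment and a late observation on the treatment just given. The SAP recognises only the first.

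Laboratory toxicity, test against reference, is a secondary safety endpoint. Liver chemistry and CPK elevations are named risks in Protocol 3.3.1 and adverse events of special interest in SAP 10.4.3. A rise that appears after the early sample would be missing from the change summary of the treatment it followed. It could also distort the change shown for the next treatment.

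**Working it through.** The plan gives no figure of its own on this point.

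**1. Periods exposed (Protocol 5.2).** A period is exposed if another period follows it.
- Part 1: 14 subjects × 1 non-final period = 14, of 14 × 2 = 28.
- Part 2: 24 subjects × 2 non-final periods = 48, of 24 × 3 = 72.

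In the planned sequences each treatment comes last equally often: 7 times in Part 1 and 8 times in Part 2. A late value is therefore planned for 14 − 7 = 7 administrations of each treatment in Part 1, and 24 − 8 = 16 of each in Part 2.

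**2. When the next Day -1 sample falls.** Hours after the preceding dose = dose-to-dose gap − lead of the sample before the next dose. The minimum gap is 7 × 24 − 4 = 164 h. The documents give no clock time for the Day -1 sample, so a lead of 12 to 24 h is assumed.

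| Gap | Hours after preceding dose | Days | Within 6 days (144 h)? |
|---|---|---|---|
| 164 h | 140 to 152 | 5.8 to 6.3 | only if lead is 20 h or more |
| 168 h | 144 to 156 | 6.0 to 6.5 | only if lead is 24 h |
| 192 h | 168 to 180 | 7.0 to 7.5 | never |

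The AE rule (SAP 10.2.1.2) works by calendar date. At a 7-day gap, Day -1 is dose date + 6, so an AE starting that day is on-treatment for the preceding dose if the rule is run per period. At 8 days it is dose date + 7 and falls outside the formula.

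**3. Effect on the next treatment's change.** Let d be the delayed rise present at Day -1, f the fraction of d still present at the next post-dose sample, and e the next treatment's own effect. With the per-period baseline:

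change = e + f·d − d = e + (f − 1)d

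With e = 0: f = 0 gives −d; f = 0.5 gives −0.5d; f = 1 gives 0; f = 1.2 gives +0.2d. The sign depends on whether the rise is subsiding, stable or growing.

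**4. Illustration with assumed ALT values.** Period 1 Day -1 is 20, Period 1 post-dose 22, Period 2 Day -1 80, Period 2 post-dose 60.
- First treatment as summarised: 22 − 20 = +2.
- Second treatment as summarised: 60 − 80 = −20 (d = 60, f = 40/60).
- Had the rise persisted at 80, the second change would be 0; had it grown to 92, it would be +12.
- A late row for the first treatment would show 80 − 20 = +60 in all three cases.

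**5. What the other displays catch.** Listings 18 to 23 are limited to Grade 2 or higher toxicities and the data of subjects who have them. In Protocol Appendix 6, Grade 2 starts at 2.5 × ULN for ALT and 6 × ULN for creatine kinase. An ALT of 80 is below Grade 2 for any ULN above 80/2.5 = 32. Such a value is listed only if the subject has some other Grade 2 or higher value, and it is an AE only if the investigator judges it clinically significant. Repeat tests are unscheduled, and the SAP leaves unscheduled visits out of summary tables.

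**The case against.** The strongest reply is that little is really lost. Listings 18 to 23 do not exclude Day -1, and Listings 19 and 21 give the whole time course for any subject with a Grade 2 or higher chemistry or haematology value. Clinically significant abnormalities are AEs, which at a 7-day gap can be charged to the preceding dose. Liver events have their own listings, and a subject who meets the liver stopping criterion before the next dose contributes no next-treatment change. All of this stands. It confines the gap mainly to rises below Grade 2 that are not AEs, and to the change tables.

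A second reply is that a Day -1 value need not belong to the earlier dose. With the 14 h half-life in Protocol 3.2, the drug remaining, 2^(−T/14), is about 0.10% at 140 h and 0.01% at 180 h. Creatinine changes are expected to reverse in washout, CPK rises are linked mainly to exercise, and subjects have left the unit in between. This is fair and is why the fix is descriptive. It does not justify omitting the value: the SAP's own windows, if run per period, treat roughly 6 days after a dose as belonging to it, and a late liver or CPK rise remains possible.

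Third, the added row would have no final-period value apart from follow-up tests prompted by an abnormal result, and balance across treatments needs complete sequences. Both limits are real and belong in a footnote.

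Finally, the column alignment of the Time and Events text leaves unclear whether the early sample is on Day 1 after dosing or at about 24 h. The conclusion is the same either way.

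**Conclusion.** The point holds for Tables 2.5 and 2.6 and is a low-cost improvement rather than a serious fault. In 14 of 28 planned subject-periods in Part 1 and 48 of 72 in Part 2, the only scheduled late laboratory value after a dose is not summarised for that dose. Safety is descriptive, so no formal conclusion depends on it.

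A reader might infer more, and the documents do not support it:
- That a delayed rise is charged to no treatment anywhere. Listings and AE reporting catch the larger or clinically significant ones.
- That the next treatment's change is always lowered. This needs f < 1.
- That 62 of 100 subject-periods (14 + 48 of 28 + 72) are affected. They are exposed; the documents give no frequency of delayed rises.
- That the sample is shown to fall outside the on-treatment window. This depends on an assumed clock time, on the actual gap, and on a window no laboratory display is said to use.
- That the per-period baseline is an error or contradicts the protocol. It is normal in a crossover, and Protocol 10.3 leaves room for it: "Baseline or pre-dose assessment is the last available assessment prior to time of the first dose unless it is specified otherwise". SAP 2.1 does not mention it, saying "There were no other changes to or deviations from the originally planned statistical analysis specified in the protocol", but that silence is not a contradiction.

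**What to change.** Keep the per-period baseline and make these additions to the SAP:

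- **10.2.1.1:** state that treatment start and stop are taken per period, and that for laboratory data the window runs to the next period's dose.
- **Tables 2.5 and 2.6:** add one row giving the next period's Day -1 value as a late post-dose value of the preceding treatment, with change from that treatment's own Day -1 baseline. The same value stays as the next period's baseline.
- **Listings 18 to 21:** label Day -1 values from Period 2 onward with the preceding treatment.
- **Footnote:** say that final periods have no such value except conditional follow-up tests, and that balance across treatments holds only if sequences are complete.

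The cost is SAP wording, some programming and one descriptive row per table. No new samples or visits are needed, and the PK analysis is untouched.
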